1. LIST OF ABBREVIATIONS

Abbreviation	Definition
AEM	Adverse Event Monitoring
AfME	Africa Middle East
ALT	Alanine Aminotransferase
AST	Aspartate Aminotransferase
BMI	Body Mass Index
BP	Blood Pressure
BUN	Blood Urea Nitrogen
CIOMS	Council for International Organizations of Medical Sciences
CRF	Case Report Form
CR	Complete Response
CSR	Case Study Report
eCRF	Electronic Case Report Form
EDC	Electronic Data Capture
EDP	Exposure during pregnancy
EIU	Exposure In-Utero
EMA	European Medicines Agency
ENCePP	European Network of Centres for Pharmacoepidemiology & Pharmacovigilance
ESMO	European Society for Medical Oncology
FKSI-19	Functional assessment of cancer therapy Kidney Symptom Index
GEP	Good Epidemiological Practice
HRQOL	Health Related Quality Of Life
ICF	Informed Consent Form
IEA	International Epidemiological Association
IEC	Independent Ethics Committee
IRB	Institutional Review Board
ISPE	International Society for Pharmacoepidemiology
ISPOR	International Society for Pharmacoeconomics & Outcomes Research
LDH	Lactic Dehydrogenase
LVEF	Left Ventricular Ejection Fraction
mRCC	metastatic Renal Cell Cancer
NIS	Non-interventional Study
NCCN	National Comprehensive Cancer Network
ORR	Objective response Rate
OS	Overall Survival
PFS	Progression Free Survival
Plt	Platelet Count
PR	Partial Response
QoL	Quality of Life
RR	Relapse Rate
SAP	Statistical Analysis Plan
SAE	Serious Adverse Events
SU	Sunitinib

Abbreviation	Definition
TTF	Time to Treatment Failure
TTR	Time to Response
VEGF	Vascular Endothelial Growth Factor
VEGFR	Vascular Endothelial Growth Factor Receptor
WBC	White Blood Cells

3. ABSTRACT

3.1. Title

Real-world clinical patterns of care and outcomes among patients in Africa Middle East (AfME) with metastatic renal cell carcinoma (mRCC) receiving Sunitinib as first line therapy (OPTIMISE).

3.2. Rationale and Background

According to the available literature, there is a gap in regards to the real world setting of care and treatment outcome for mRCC, especially in the Middle East and Africa region.

SU has become the standard of care (used as first-line treatment) in many countries as it has the most robust data in the first-line treatment of mRCC. It is also recommended as first line treatment in the NCCN and ESMO guidelines.

In order to understand how care is translated into positive treatment outcomes in the broader mRCC patient population and whether there are differences in outcome associated with various treatment patterns, a prospective observational study is necessary. This study will elucidate for the first time the patterns of care and associated outcomes in Africa Middle East patients with mRCC.

3.3. Research Objective, Endpoints and Questions

3.3.1. Research Questions

OPTIMISE study objectives are dual and aim primarily to increase the knowledge regarding the outcomes from SU use on one hand; and outcomes from the combined SU- 2nd line sequence on the other hand in real life clinical practice. This will be addressed in many countries across AfME and in individual country cohorts to understand specificities and differences in use and outcomes.

3.3.2. Objectives

OPTIMISE is designed to provide knowledge regarding the use of the SU as 1st line treatment and 2nd line SU-different sequence with respect to efficacy outcomes, adverse events, and health related QoL in the real life setting.

Primary Objective:

- To assess the impact of SU as 1st line treatment on PFS and on TTF for patients with adv/mRCC.

Secondary Objective:

- To assess the ORR for adv/mRCC patients receiving SU as 1st line treatment.
- To describe the usage of different doses of SU in these patients in terms of: dosing change, dosing schedules and the average dose received during the SU period treatment.

- To assess the impact of the 2nd line sequence SU- different treatment on combined PFS and TTF for patients with adv/mRCC and according to the second line post SU treatment (TKI,mTOR).
- To describe the safety of 2nd line SU-different sequence treatment and the tolerability of patients receiving it.
- To measure Quality of Life (QoL).

3.3.3. End-points

Primary End-point:

1. Progression Free Survival (PFS) for patients with ad/mRCC receiving SU.

PFS is defined as: the time from when the patient receives the first dose of SU to the time of progression or death due to any cause, which occurs first.

2. Time to Treatment Failure (TTF) for SU 1st line.

TTF is defined as: from when the patient receives the first dose of SU to the time of SU discontinuation (date completed by the physician).

Secondary End-point:

1. Objective Response Rate (OOR) for adv/mRCC patients receiving SU as 1st line treatment.

ORR is defined as the percentage of patients with confirmed CR or confirmed PR according to RECIST criteria v1.1.

2. Description of SU real life usage of doses across all centers, including description of treatment schedules (dose change, dose schedule, average dose received during the period treatment).

3. Combined PFS for patients with ad/mRCC receiving the 2nd line sequence SU- different treatment.

Combined PFS is defined as: the time from when the patients receives the first dose of SU as first line, until progression or death due to any cause while on the 2nd line treatment, whichever occurs first during the 2nd line sequence treatment.

4. Combined TTF for the SU-2nd line sequence.

Combined TTF is defined: as the time from when the patient receives the first dose with SU as first line, to the time of 2nd line sequence discontinuation (date completed by the physician).

5. OS for adv/mRCC patients receiving SU as first line followed by 2nd line as measured from date of first SU dose to the date of death of any cause. The OS median and the overall survival at month 24 (24 months OS) will be measured.
6. If possible, efficacy parameters (PFS, OS) for the combined 1st line SU- 2nd line sequences according to the second line post SU (other than SU-AXI):
 - SU in 1st line-Axitinib TKI in 2nd line.
 - SU in 1st line- other TKI in 2nd line (sorafenib, pazopanib).
 - SU in 1st line/mTOR in 2nd line (temsirolimus, everolimus).
7. Safety description with AE listing in patients receiving SU: frequencies of patients experiencing at least one AE will be displayed by body system.
8. QoL using the questionnaire Functional Assessment of Cancer Therapy-Kidney Symptom Index 19 (FKSI-19).

CCI

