3.4. Study Design and Study Population

OPTIMISE is an international (AfME), prospective, non-interventional, non-controlled, observational multicenter study.

Patients would be enrolled from several AfME countries including Algeria, Morocco, Tunisia, Egypt, UAE, Qatar & South Africa.

Investigators will be specialists in charge of adv/mRCC. These sites involved (at least when performing feasibility) will be representative of their respective countries in terms of practice. Participating physicians will not be influenced in their decision making and routine proceedings in any way.

Primary outcome measure will assess progression free survival (PFS) in patients receiving the SU and in patients receiving a second line treatment post SU; as well as TTF for patients with adv/mRCC.

Patients will be enrolled when they start a treatment with SU on 1st line. Patients enrolled at SU initiation, will be followed-up whatever the post 2nd line SU- different sequence treatment is (AXI, other drugs, no further active treatment, (supportive care)). The possible 1st and 2nd line sequences of treatment under investigation (ie, patient pools) will be ([Figure 1](#)):

- SU-AXI.
- SU- other second line treatment (sorafenib, pazopanib, everolimus, temsirolimus, other).
- SU- not further active treatment (supportive care).

The study will include a prospective data collection:

- Prospective data will be collected for all patients enrolled in the study at SU-1st line level, irrespective of 2nd line sequence treatment, or no further active treatment.
- Prospective data in terms of medical treatment records will be collected for all 2nd line patients.

The inclusion period of eligible patients is planned for 12 months, with minimum of 1 year follow-up period. Patients will be followed-up from their enrollment to the end of the study follow-up period.

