5. MILESTONES

Milestone	Planned date
Completion of feasibility assessment	Aug-2016
Start of data collection FSFV	Sep-2016
End of data collection, last subject last visit (LSLV)	Sep-2019
Final study report	Jan-2020

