6.1. Selection of First-Line Treatment

6.1.1. First-Line Treatment in Patients With Favorable- to Intermediate-Risk Clear Cell mRCC

Currently, Phase III data originating from four randomized trials support the use of three molecules in the first-line setting, ie, Sunitinib,^{5,6} pazopanib,⁷ and bevacizumab, in combination with interferon- α .^{8,9} The criteria for choosing between Sunitinib and pazopanib currently represent the hottest topic of debate. Its importance prompted the design and conduct of the first head-to-head Phase III trial comparing two first-line treatment alternatives for mRCC patients.¹⁰

A head-to-head prospective Phase III trial of Sunitinib and pazopanib [COMPARZ], ClinicalTrials.gov identifier NCT00720941¹⁰ the randomized design rested on the non-inferiority comparative effectiveness of 800 mg once daily continuous dosing of pazopanib relative to 50 mg once daily 4/2 weeks dosing of sunitinib. Although there is no doubt that direct comparison of Sunitinib versus pazopanib represents an effort aimed at providing evidence data in regards to two management alternatives for clear cell mRCC patients, many questions pertaining to study results and their interpretation remain unanswered.

The observation of differences in patterns of care between community and academic practice dovetails with other retrospective reports. Choueiri et al. published a series of 144 RCC patients from two tertiary oncology centers in the US. Patients were treated with Sunitinib, sorafenib, or bevacizumab from 2003 to 2008. Treatment patterns, response rates, and adverse events were described.¹² Similar data were obtained from a retrospective review of 250 patients with mRCC treated at 18 community oncology clinics. Differences in outcomes between these two studies included median duration of first line therapy for both Sunitinib (5.9 months in the community vs. 10.5 months in the academic centers) and sorafenib (5.5 vs. 8.1 months). In addition, patients in the community were more likely to receive lower doses of Sunitinib and sorafenib and were more likely to have dose reductions and interruptions than patient in the academic centers. These differences in practice patterns are an important area of further research and may lead to the understanding of more optimal treatment regimens for patients.¹³

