8.5.3. Follow-up Phase

For each subject, after treatment, there would be two follow-up visits (Visit 6-7) in one year, one visit every 6 months (month 18 and 24).

- Concomitant medications (a window period of 28 days prior to the start of the study treatment, during the study and up to 28 days post the last dose of treatment applies).
- Adverse Events Assessment.
- Update in Disease Status (including PFS, RR, TTR, TTF, OS).
- Update in Treatment Status/ Change in therapy.
- Reporting of routine labs collected.

- Performance Status (ECOG), weight (BMI) and blood pressure.
- QOL questionnaire (FKSI 19) ([Appendix 1](#)).

In case of no treatment failure till month 12, more treatment visits will be scheduled until SU discontinuation.

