8.1. Efficacy analyses

8.1.1. Survival analyses

▪ Role:

- To meet primary and secondary objectives
- To assess the impact of SU as a first line therapy on progression free survival (PFS) and on time to treatment failure (TTF) for patients with adv/mRCC in real life setting;
- To assess the impact of the SU–other sequence on combined PFS and TTF for patients with adv/mRCC.
- To assess the Overall Survival (OS) (OS median and 24-month OS) for adv/mRCC patients receiving SU in first line followed by other sequence in 2nd line;
- To assess the time to strategy failure (TSF) for adv/mRCC patients receiving the SU–other sequence;
- To assess PFS and OS for the combined 1st line SU – 2nd line sequences according to the second line post SU (TKI, mTOR) treatment; (specific objective – “SU – TKI/mTOR” patients)

▪ Population:

- “SU – other sequence” patients
- “SU – TKI / mTOR” patients

▪ Endpoints:

- Progression Free Survival (PFS)
- Combined PFS
- Time to Treatment Failure (TTF)
- Combined TTF
- Time to Strategy Failure (TSF)

- Overall Survival (median OS and 24-month OS rate)
- **Subgroups:**
- Type of 2nd line treatment post SU: “SU – TKI / mTOR” patients (**SUT-TKI and SUT-mTOR**)
(only combined PFS and OS endpoints)
- **Statistical methods:** Survival analysis methods.
- **Method for handling missing values:** see guideline in chapter 7.

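### Combined PFS and combined TTF depend on starting second line before follow-up closes, so patients still on SU drop out and the second-line-only median does not describe the strategy

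*Protocol*

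**What the plan says.** Protocol 3.3.3 lists, as secondary end-point 3, "Combined PFS for patients with ad/mRCC receiving the 2nd line sequence SU- different treatment", measured from the first SU dose to progression or death on second line. End-point 4, combined TTF, also starts at the first SU dose and runs "to the time of 2nd line sequence discontinuation (date completed by the physician". SAP Appendix 3 repeats both definitions.

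SAP 8.1.1 gives the role "To assess the impact of the SU–other sequence on combined PFS and TTF for patients with adv/mRCC" and lists two populations, SU–other sequence and SU–TKI/mTOR, both named by what came after SU. The three patient pools in Protocol 3.4 (SU then axitinib, SU then another drug, SU then supportive care) all require SU to have stopped.

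Follow-up is described in several ways:
- Protocol 3.4: "The inclusion period of eligible patients is planned for 12 months, with minimum of 1 year follow-up period", and "Patients will be followed-up from their enrollment to the end of the study follow-up period".
- Protocol 8.4.1 and 8.5.3: last scheduled visit at month 24.
- Protocol 5: data collection from Sep-2016 to Sep-2019.
- Protocol 8.5.3: "In case of no treatment failure till month 12, more treatment visits will be scheduled until SU discontinuation". No extension beyond the end of the study is stated.

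SAP 7.4 names Kaplan-Meier as the method. SAP section 6 says that all patients are included and right-censored, but of the primary endpoint.

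**The concern.** The time being measured includes the SU period, yet entry to the analysis requires that period to be over. A patient doing well on SU at close has the longest sequence time but belongs to none of the named groups. Kaplan-Meier can censor only patients who are in the data set, so it cannot correct for those kept out of it. This is right truncation on part of the outcome.

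Protocol 3.3.1 makes the SU–second-line sequence one of two aims and wants outcomes compared across country cohorts. The distortion grows with SU duration and shrinks with length of follow-up. Countries with different SU duration, or studies with different follow-up, would therefore differ in their reported combined medians partly for reasons unrelated to the treatment.

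**Working it through.** **The plan's own figure.** The documents give no design figure for the combined endpoints. The only one is the ORR precision in Protocol 8.7. It reproduces (1.96 × √(0.37 × 0.63 / 140) = 0.080) and does not bear on this point.

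**Inputs.**
- Median SU time: "5.9 months in the community vs. 10.5 months in the academic centers", background figures in Protocol 6.1.1, used as a range.
- Potential follow-up C: uniform 12–24 months (12-month inclusion plus a 1-year minimum), fixed 24 months (visit schedule), or uniform 24–36 months (36-month calendar less 12-month inclusion).
- Assumed, not in the documents: exponential SU time T1; second line starting when SU stops; exponential second-line time T2 with median 3, 5 or 8 months, independent of T1.

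**Step 1: share still on SU at close.** With λ = ln 2 / median, the share is exp(−24λ) for fixed 24 months. For uniform follow-up from a to a + 12 it is [exp(−aλ) − exp(−(a+12)λ)] / (12λ). Examples: exp(−ln 2 × 24/10.5) = 0.205 and exp(−ln 2 × 24/5.9) = 0.060. For 12–24 months at a median of 10.5, (0.453 − 0.205)/0.792 = 0.313.

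**Step 2: effect on the median.** I simulated 400,000 patients per scenario. The median of T1 + T2 in everyone was compared with the Kaplan-Meier median of min(T1 + T2, C) in those with T1 < C. With a 5-month second-line median:

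| SU median | Follow-up (months) | Still on SU at close (of 140) | Full-sequence median | Second-line starters only | Difference |
|---|---|---|---|---|---|
| 5.9 | 12–24 | 13.1% (18) | 13.2 | 11.6 | −12% |
| 5.9 | 24 | 6.0% (8) | 13.2 | 12.4 | −6% |
| 5.9 | 24–36 | 3.2% (4) | 13.2 | 12.8 | −3% |
| 10.5 | 12–24 | 31.3% (44) | 18.2 | 13.1 | −28% |
| 10.5 | 24 | 20.5% (29) | 18.2 | 14.8 | −19% |
| 10.5 | 24–36 | 14.2% (20) | 18.2 | 15.8 | −13% |

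Across second-line medians of 3 to 8 months, the shortfall is 3–12% (0.3 to 2.0 months) at an SU median of 5.9 and 13–29% (2.1 to 5.9 months) at 10.5. It is negative in all 18 scenarios. In this model, where everyone eventually reaches second line, adding back those still on SU as censored returns the full-sequence median.

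The gap between the two SU settings is 18.2 − 13.2 = 5.0 months. Among second-line starters it shows as 13.1 − 11.6 = 1.5, 14.8 − 12.4 = 2.4 or 15.8 − 12.8 = 3.0 months.

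**Step 3: selections in the other direction** (5-month second line).
- SAP 4.1 limits the efficacy population to patients followed for at least 6 months. Requiring T1 + T2 ≥ 6 months, an upper-bound stand-in, lifts the second-line-only median to 13.8–15.1 at an SU median of 5.9 (above 13.2) and to 15.0–17.7 at 10.5 (still below 18.2).
- Patients who die on SU, or stop without second line, are also left out. If 40% or 60% reach second line (assumed, unrelated to SU time) and the others end the sequence at T1, the median in all SU starters is about 8.6 or 10.1 months at 5.9, against 11.6–12.8 in second-line starters. At 10.5 it is 13.6 or 15.2, against 13.1–15.8.

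**The case against.** *A reader might infer that the reported combined medians will simply be too low.* The documents do not support that. Step 3 shows two selections that raise the median. With the shorter SU duration, either can reverse the sign, the second one by changing the comparison to all SU starters. This objection stands: the downward effect holds only relative to patients who would eventually receive second line.

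*Exclusion is one reading.* SAP Appendix 3 defines the combined endpoints without restricting the population. SAP 8.1.1 lists the same groups for an analysis that also covers first-line PFS and TTF, and 8.1.2 calls SU–other sequence the study population. The shell table in SAP 9.3 places supportive care under second-line therapy, so even that group's status is unsettled. This makes the meaning unclear, but it does not remove the restriction written into Protocol end-point 3.

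*A reader might infer that the plan has no rule for patients still on SU.* That cannot be asserted. The SAP text between the subgroup section and the safety endpoints is redacted or lost, and terms analysed later, such as time to strategy failure, have no visible definition. The point rests instead on the population wording that can be seen.

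*The largest figures need the shortest follow-up and the longest SU duration.* That is correct. On the Sep-2016 to Sep-2019 calendar the effect is 3–14%, and the extra visits until SU stops ease it further if they continue to the end of the study. Protocol 8.11 also limits the study to hypothesis generation.

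**Conclusion.** The point holds as a cheap improvement. As the visible definitions read, inclusion in combined PFS and combined TTF depends on SU ending and second line starting before close. Taken alone, and relative to patients who would eventually receive second line, this lowers the median by 3–12% (SU median 5.9 months) or 13–29% (10.5 months). The size depends on which follow-up statement applies and on the stated assumptions.

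The net direction is not fixed, because losing patients who never reach second line, and the 6-month efficacy set if applied, push the other way. Opposing selections of unknown size do not validate the estimate. The second-line-only median cannot be read as the result of the SU–second-line strategy.

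A reader might also infer that analysing all SU starters recovers the second-line median (18.2 months in the example). It does so only if every patient reaches second line. Otherwise it estimates a different quantity, as Step 3 shows.

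**What to change.** In Protocol 3.3.3 (end-points 3 and 4) and SAP 8.1.1:

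1. State the target population for combined PFS and combined TTF.
2. Make the lead estimate one in all patients who start SU, with those still on SU censored at last contact. Count death on SU, or stopping SU without second line, as the end of the sequence, or treat it as a competing event with Aalen-Johansen estimates.
3. Keep the second-line-only Kaplan-Meier curve as descriptive, labelled *patients who started second line within follow-up*, with the number still on SU at cut-off beside it.
4. Say whether the 6-month efficacy set applies to these endpoints, and reconcile the follow-up statements.

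The cost is endpoint and SAP wording plus one added analysis. Protocol 3.4 already collects prospective data on every enrolled patient whatever follows SU, so no new patients or visits are needed. The downside is that the lead estimate describes the strategy in all SU starters, not the experience of second-line recipients, and must not be presented as recovering their median.

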3.5. Setting

The study will enroll patients according to the eligibility criteria in participating countries across Africa Middle East. The recruiting centers will be representative of each country involved in terms of care management systems, of size and of practices (at least when performing feasibility).

Any patient who meets the eligibility criteria will be invited to participate in the study with no selection by the investigators. The enrollment visit will be performed at the time of the patients' inclusion, after the patients' acceptance of enrollment in the study.

Data will come from medical records and will be collected in routine clinical practice. The enrollment visit will comprise a first section on patients' eligibility for every patient.

Follow-up will be ensured during visits in the context of usual patients' care management (non-interventional study). As long as the patients are treated with SU, AXI, other TKI (sorafenib, pazopanib everolimus, temsirolimus, other) or no further active treatment (supportive care), every visit to the center will be recorded. In accordance with ESMO guidelines and physicians clinical practice is real life, follow-up visits are approximately expected as below:

- During SU treatment: every 6 weeks (every cycle) with tumor assessment approximately every 3 months with respect to the clinical practice.
- When patients come off SU treatment: they will be followed-up every 6 months for survival until the end of the study.
- A deviation of +/- 6 weeks (1.5 months) is acceptable window for the follow-up visits.

Because of the inclusion criteria (patients being treated with SU in 1st line according to the approved therapeutic indication), the medication prescribed within the regular practice of the physician. Because of the non-interventional nature of the study, there will be no specific requirements in regards to the treatment process. The physician will determine dosage and duration of the treatment as guided by the local approved country. Prescribing information will be according to his assessment of the individual therapeutic needs of the patient.

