5.5. Covariates

- In case of multivariate analyses, baseline characteristics will possibly be used as covariates.
- The final covariates will be selected according to the selection strategy of variables defined in the part 7.6.
- Possible, but not exclusive, baseline covariates related to SU initiation will be limited because of a retrospective part of the data collection, with:
 - Age and sex;
 - ECOG (0, 1, 2, 3, 4), Karnofsky performance status
 - MSKCC risk factors (Favorable, Intermediate, Poor)

- Medical history of hypertension (Yes, No)
- Delay from diagnosis (< 1 year from diagnosis to first metastasis detection/ \geq 1 year)
- Nephrectomy (Yes, No)
- Number of metastatic sites
- The covariates identified previously will be also explored and act as baseline for second line treatment initiation. In this case, other covariates will be:
 - The response to SU treatment in 1st line;
 - Duration of SU treatment, PFS;
 - Previous treatments for primary tumor (surgery, radiotherapy, other);
 - Additional anti-tumor treatments;

6. Handling missing values

- The majority of data will be collected with a website (except for FKSI-19 questionnaires).
- In this website, the input of certain data will be obligatory, limiting the number of missing values, particularly for endpoints.
- Regarding the descriptive analyses of each variable, it will be based on the available data (“observed-case analysis”), considering missing data as non-informative.
- The number of missing data will be documented for each analysis.
- The analysis of the primary endpoint is a survival analysis which is known to efficiently handle missing data: All patients are included in the analysis and missing data are called right-censored data.
- In case of absence of 20% data and over, for a main parameter such as ORR rate, the Hot-deck imputation method could be used. With this method, the missing value is replaced by the observed value of a patient with similar characteristics $X_1, X_2 \dots X_k$. If it does not exist such similar patient, the missing value will be amputated
- A sensitivity analysis will be conducted by the imputation of extreme values. In the one hand, analysis in the most unfavorable situation (i.e. missing data considered as failure) and in the other hand, analysis in the most favorable situation, i.e. missing data considered as success (e.g. for ORR, success is to be responder).

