7.4. Survival analysis methods

- The survival functions for PFS, TTF, TSF, and OS will be estimated with the Kaplan-Meier method. The survival function $S(t)$ is the probability that the event (treatment discontinuation, death or progression) does not occur before a specified time.
- This method will be applied to derive, survival curves, median event time and a 95% confidence interval for the median survival time (time at which half the analyzed patients have presented the event).
- Survival curves will give an idea of whether or not the groups are proportional (i.e. the survival functions are approximately parallel).
- For OS, the share of patients alive at 24 months will also be measured.
- The log-rank test of equality across strata will be used to compare survival curves for categorical variables (sub-groups of interest).
- For continuous variables, a univariate Cox proportional hazard regression will be used.
- For analyses of prognostic factors of survival time, multivariate Cox proportional hazard regressions will be performed.

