Appendix 3: List of covariate and outcomes in the study

Variable	Role	Operational definition
Age	Covariate	Defined as the date of birth of the participant
Gender	Covariate	Defined as the male or female sex
Ethnicity	Covariate	Defined as race of Middle Eastern, Indian, Caucasian or African descendant
ECOG	Covariate	The ECOG Scale of Performance Status describes a patient's level of functioning in terms of their ability to care for themselves, daily activity, and physical ability (walking, working, etc.)
Number of metastatic sites	Covariate	Total number of site where metastasis is detected
Nephrectomy	Covariate	Surgical removal of the kidney
MSKCC risk	Covariate	The MSKCC risk system stratifies patients with mRCC into poor-, intermediate- and favorable-risk categories based on the number of adverse clinical and laboratory parameters present
Hypertension	Covariate	Presence of high systolic blood pressure >13mmHg
Previous medical treatment	Covariate	Presence of medical treatment related to the disease prior to SU initiation
PFS	Outcome	The PFS will be defined as the time from when the patient receives the first dose of SU to the time of progression or death due to any cause, whichever occurs first
OS	Outcome	OS defined as the time from date of first SU dose to the date of death of any cause.
ORR	Outcome	The objective response rate is the percentage of patients with a complete response (CR) or a partial response (PR) according to RECIST 1.1 criteria as best response, over the SU treatment period.
TTF	Outcome	TTF is defined as the time from when the patient receives the first dose of treatment to the date of SU discontinuation
Combined PFS	Outcome	The time from when the patients receives the first dose of SU as first line, until progression or death due to any cause while on the 2nd line treatment, whichever occurs first during the 2nd line sequence treatment.
Combined TTF	Outcome	The time from when the patient receives the first dose with SU as first line, to the time of 2nd line sequence discontinuation

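### Combined PFS leaves out progression and death after second-line treatment stops; if those patients are censored, the censoring is dependent and the median is probably too long

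*Protocol*

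**What the plan says.** Protocol 3.3.3 (secondary end-point 3) defines combined PFS from the first SU dose "until progression or death due to any cause while on the 2nd line treatment", and then adds a closing limit to the same effect. SAP Appendix 3 carries the same definition, including the closing limit "whichever occurs first during the 2nd line sequence treatment". The on-treatment condition is therefore stated twice in each document, and it applies to death as well as progression.

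Two other end-points in the same protocol list show the contrast:

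- First-line PFS runs "to the time of progression or death due to any cause, which occurs first", with no condition that SU is still being taken.
- Combined TTF runs "to the time of 2nd line sequence discontinuation (date completed by the physician", so there the stop is itself the event.

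On method, SAP 7.4 says "The survival functions for PFS, TTF, TSF, and OS will be estimated with the Kaplan-Meier method". The only readable general statement on censoring is in SAP section 6, written for the primary endpoint: "All patients are included in the analysis and missing data are called right-censored data". No readable sentence says what happens in combined PFS to a patient who stops second line without progression. The SAP text between 4.2 and the safety endpoints is redacted or not shown.

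After SU, protocol 3.5 says of patients that "they will be followed-up every 6 months for survival until the end of the study". Protocol 8.4.1 and 8.5.3 also list disease-status updates at months 18 and 24.

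**The concern.** A patient who stops second line for toxicity or decline, and dies or progresses afterwards, drops out of the event count. Kaplan-Meier assumes that people censored at a given time have the same future risk as those still at risk. That is doubtful here for two reasons. Patients who stop because they are doing badly may have a higher risk afterwards. And because the clock starts at first SU dose, the risk set at any time also contains patients still on SU, who cannot yet have a combined-PFS event.

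Combined PFS is also the endpoint for comparing sequences. SAP 4.2.1 plans a comparison of axitinib, other TKI and mTOR inhibitors after SU, SAP 8.1.1 assigns combined PFS and OS to the analysis by second-line type, and SAP 7.4 names the log-rank test. If one second-line drug is stopped early more often than another, the definition treats the two sequences differently for a reason unrelated to disease control.

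**Working it through.** **1. The plan's own figures.** The documents give no median, event count or precision for combined PFS, so there is nothing to reproduce on this point. The only design figure is the ORR margin: 1.96 × √(0.37 × 0.63 / 140) = 0.080. It reproduces, but has no bearing here.

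**2. Why the censoring is dependent.** Let T1 be the time from first SU dose to second-line start, X the time from second-line start to progression or death, and S the time from second-line start to stopping the drug.

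- Event time = T1 + X. Censoring time = T1 + S. They share T1, so they are correlated even if X and S are independent.
- With a constant second-line hazard λ2, the hazard that Kaplan-Meier sees at time t is λ2 × π(t), where π(t) is the share of the risk set already on second line. Patients still on SU contribute zero.
- Censoring at the stop removes people only from the second-line part of the risk set. π(t) falls, the estimated hazard falls, and the curve is too high, even if the hazard does not change at the stop.
- A higher hazard after stopping adds to this. A sufficiently lower one offsets or reverses it.

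**3. Simulation inputs.**

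- From the protocol: SU median 5.9 or 10.5 months (treatment durations cited in 6.1.1). Follow-up of 24 to 36 months: data collection from Sep-2016 to Sep-2019 is 36 months, less 12 months of accrual for the last patient. The protocol promises only a minimum of 1 year.
- Assumed, with no source in the documents: second-line median 4 to 8 months; a fraction f of 15 to 30% stopping before an event; hazard after stopping 0.25 to 2 times the on-treatment hazard.
- Model: exponential times, λ2 = ln 2 / median, stop rate λs = λ2 × f / (1 - f). For a median of 4 and f = 0.30: λ2 = 0.173, λs = 0.074, and 0.074 / (0.074 + 0.173) = 0.30.
- At least 200,000 patients per setting. Only patients who start second line are analysed, under both rules, so that restriction does not create the difference.

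**4. Results.** Kaplan-Meier median with censoring at the stop, minus the median with all events counted, in months:

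| Hazard after stopping | Second-line median 4-8, f 15-30% | Wider grid: median 4 or 7, f 10-40% |
|---|---|---|
| × 0.25 | -1.2 to -0.2 | -1.8 to -0.1 |
| × 0.5 | -0.3 to +0.7 | -0.2 to +1.3 |
| × 1 | +0.3 to +1.7 | +0.2 to +2.8 |
| × 2 | +0.8 to +2.6 | +0.5 to +3.8 |

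One setting in full (SU median 10.5, second line 4, f = 30%), all events against censoring at the stop: 15.5 and 16.2 months at × 0.5; 14.5 and 16.3 at × 1; 13.7 and 16.3 at × 2. Simulation error and rounding are about 0.1 month. With no end to follow-up, the first-column ranges at × 1 and × 2 become +0.4 to +2.8 and +0.8 to +3.7.

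**5. Effect on a comparison.** Take two sequences with the same on-drug hazard (SU median 10.5, second line 6, hazard doubled after stopping), one with 10% stopping early and the other with 30%.

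| | All events, 10% stop | All events, 30% stop | Censored at stop, 10% | Censored at stop, 30% |
|---|---|---|---|---|
| No end to follow-up | 19.3 | 18.5 | 20.2 | 22.1 |
| 24-36 months | 16.7 | 16.1 | 17.4 | 18.5 |

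In this example the order of the two sequences reverses.

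**The case against.** **The SAP may contain a rule that cannot be read.** Time to strategy failure is analysed in SAP 7.4 and 8.1.1 but defined nowhere readable, so endpoint definitions probably sat in the lost text. A reader might infer that the plan orders censoring at the second-line stop. No readable sentence says so, and the gap is not a fault of the plan. This stands. What remains is that both readable definitions exclude the later event, and a hidden censoring rule could not turn it into an event without contradicting them.

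**The wording may only identify which progression counts**, meaning the one after second-line start and not the one on SU. That is possible, and would bring the definition close to the fix below. It is the weaker reading, because the limit also covers death and is stated twice. If it was the intention, the text still needs the same clarification.

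**The direction is not certain.** A reader might conclude outright that the combined median is overstated. The documents give neither the share of patients who stop second line early nor their later hazard, and at half the hazard or less the bias is mixed or reversed. Only a likely overstatement can be claimed.

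**The consequence is limited.** This is a secondary endpoint, the protocol makes the analysis by sequence conditional on feasibility, and protocol 8.11 calls the study hypothesis-generating. First-line PFS is untouched, combined TTF captures stopping, and OS captures later deaths. All true. But combined-sequence outcomes are one of the two aims in protocol 3.3.1, and a descriptive estimate should still measure what its name says.

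**The fix is not free of problems.** Tumour assessment about every 3 months is described only during SU, and some later events will follow a third line. This stands and is addressed in the fix.

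**Conclusion.** The point holds in conditional form. As written, combined PFS excludes progression and death after second line stops. Kaplan-Meier can then treat these patients only as censored, and that censoring is dependent because the clock includes the SU period. The median is likely to be too long and the comparison by second-line type can be distorted.

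The size is an illustration, not an estimate for this study: roughly a third of a month to two and a half months if the hazard after stopping is equal to or double that on treatment, and around zero or negative if it is half or less. Of the inputs, only the SU medians and the follow-up window come from the protocol. An unchanged or higher hazard is the more plausible case where patients stop because of decline, but that is a judgement and not something the documents show.

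**What to change.** In protocol 3.3.3 and SAP Appendix 3, define combined PFS as the time from first SU dose to the first progression after second-line start, or death from any cause, whether or not second line has been stopped. Then:

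- censor patients without an event at their last disease assessment;
- state how events after a later line of therapy are handled;
- keep the on-treatment version as a sensitivity analysis, with its censoring rule written out.

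The cost is mainly wording, since survival and disease status are already collected after treatment. There are three limits. Progression is assessed less often after SU, so those dates will be coarser and some progressions may be missed. Some counted events will follow later therapy. And a patient who stops and has no further assessment may still be censored near the stop, so the change reduces the dependence without removing it. Comparing the two versions would show how much the choice matters.
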